1.1. Burden of Major Depressive Disorder and the Decisional Dilemma

Major Depressive Disorder (MDD) affects approximately 10% of the adult population in the United States,¹ and according to the World Health Organization, MDD is now the leading cause of disability worldwide.² The chronic course of the illness, which is characterized either by unremitting symptoms and dysfunction or repeated depressive episodes interspersed with periods of remission,^{3,4} significantly contributes to the personal and public health costs of the disease, which total over \$210 billion per year in the US alone.⁵ The relative effectiveness of medications for the treatment of MDD are comparable to those for other chronic medical conditions.⁶⁻⁸ However, outcomes in clinical practice continue to be poor.⁹ This is related in part to the decisional dilemma faced by clinicians and patients in determining which antidepressant is right for which patient.¹⁰ Although extensive data indicate that there are no meaningful differences among second generation antidepressants (see below), large community trials such as the Sequenced Treatment Alternatives to Relieve Depression (STAR*D) trial clearly indicate that only a minority of patients respond to the initial antidepressant, and most patients require several trials of medications to achieve response.^{6,11,12} Thus, while antidepressants are equally effective on average, response for a given patient is very antidepressant specific, leaving clinicians and patients guessing as to which drug is the best choice. This decisional dilemma results in a trial and error process of antidepressant selection, which can undermine the patient's confidence in the decision-making process, and ultimately contribute to multiple treatment trials, ineffective medications taken too long, treatments switched too early, or patients simply dropping out of care. This process also may inadvertently lead to patients being labeled treatment resistant, even when effective treatments may exist for them. Hence, reducing the decisional dilemma regarding antidepressant choice in primary care will increase the effectiveness of currently available antidepressant medications.

1.2. Current Practice Guidelines for Antidepressant Prescription and the Critical Evidence Gap

Based on an Executive Summary by the Effective Health Care Program of the Agency for Healthcare Research and Quality, which performed a comparative effectiveness review of second generation antidepressants, “*no substantial differences in efficacy exist among second generation antidepressants for the treatment of MDD*”.¹³ Accordingly, the most recent practice guidelines from the American Psychiatric Association recommend: “*Because the effectiveness of antidepressant medications is generally comparable between classes and within classes of medications, the initial selection of an antidepressant medication will largely be based on the anticipated side effects, the safety or tolerability of these side effects for the individual patient, pharmacological properties of the medication (e.g., half-life, actions on cytochrome P450 enzymes, other drug interactions), and additional factors such as medication response in prior episodes, cost, and patient preference.*”¹⁰ However, there is no empirical evidence that any of these or other clinical variables (such as baseline symptom severity, age of onset, presence of insomnia, chronicity, atypical or melancholic features) can meaningfully guide selection of one antidepressant medication over another.¹⁴⁻¹⁹ As a consequence, a critical evidence gap exists regarding how to decide which antidepressant will be most effective for a given patient. Because of this evidence gap, patients and providers face a decisional uncertainty that can undermine treatment effectiveness and patient engagement in the treatment process.

1.3. Filling the Critical Evidence Gap: Inflammation as a Predictor of Antidepressant Treatment Response

Data indicate that inflammation plays an important role in the response to antidepressants.²⁰⁻²⁴ A significant percentage of depressed patients exhibit increased inflammation,²⁵ and studies have shown that increased biomarkers of inflammation including c-reactive protein (CRP) can predict response to antidepressant treatment, including the prediction of differential response to different types of antidepressants.^{21-24,26} Relevant to the mechanisms by which inflammation can affect antidepressant response, inflammatory cytokines and their signaling pathways have been shown to increase the expression and function of the transporters for serotonin,²⁷ thereby potentially undermining the effects of selective serotonin reuptake inhibitors (SSRIs), which act in large part by blocking these transporters.²⁸ Moreover, data from both laboratory animals and humans have demonstrated that inflammatory cytokines reduce dopamine neurotransmission and inhibit dopamine-mediated reward circuits in the brain that are associated with anhedonia, a core symptom of depression.²⁹ Interestingly, administration of medications that increase dopamine signaling have been shown to reverse anhedonic symptoms in laboratory animals exposed to inflammatory cytokines.³⁰ Taken together, these translational studies strongly suggest that patients with increased inflammation are less likely respond to SSRIs and are more likely respond to drugs that augment dopamine.

1.4. Inflammatory Biomarkers Can Reduce Decisional Uncertainty and Fill the Critical Evidence Gap

In the absence of data demonstrating differential efficacy among antidepressants coupled with lack of predictive power of clinical variables, there is a critical evidence gap regarding the initial choice of currently available antidepressants.³¹⁻³³ Consistent with the translational studies described above, biomarkers of inflammation may fill this gap, given that they have been shown to be effective in predicting differential response to antidepressant subtypes in MDD.³⁴⁻³⁷ Indeed, CRP, a clinically available and inexpensive biomarker of systemic inflammation, has been shown to predict differential response to currently available antidepressants in post hoc analyses of two large community studies of over 300 patients. For example, in a study conducted by our group, MDD patients with high CRP ($\geq 1\text{mg/L}$) were found to respond better to the dopamine reuptake inhibitor bupropion in combination with escitalopram compared to patients treated with escitalopram alone, who responded better when CRP concentrations were low ($<1\text{mg/L}$).²² While systematic reviews and meta-analyses have failed to find significant differences in treatment outcomes in head-to-head comparisons of SSRIs and bupropion,^{38,39} the above-mentioned differential treatment response to an SSRI versus bupropion based on CRP level clearly demonstrates a heterogeneity in treatment effects (HTE). Hence, superiority of antidepressant selection informed by point-of-care (POC) CRP testing over the current practice of using clinical variables can reduce the decisional uncertainty of choosing the right antidepressant compared to the currently used “trial and error” process, ultimately closing the evidence gap and increasing the effectiveness of currently available antidepressant medications.

2. Introduction and Purpose

2.1. Study Overview

Despite the large socioeconomic impact of major depressive disorder (MDD), our ability to provide optimal antidepressant treatment is significantly limited. The lack of consistent clinical or laboratory predictors of response to antidepressants remains a major challenge. Currently, no biomarker is used in clinical care to aid in the selection of treatment, and finding the right medication for people suffering from MDD still relies on a “trial-and-error” method. There is an urgent need to better predict differential response to antidepressants.

The main objective of the proposed study is to evaluate the use of POC CRP as a predictor of differential antidepressant response (escitalopram versus bupropion extended-release [XL]) in individuals with MDD. Additionally, two optional sub-studies will be available for participants to enroll in.

The first sub-study will evaluate if capillary blood obtained via finger prick can be used for the POC CRP test instead of venous blood. Hence, our proposed study results have the potential to markedly impact antidepressant selection in routine clinical practice and allow treatment providers and patients to choose an antidepressant that is more likely to result in favorable treatment outcomes. If favorable, this study would also support personalized selection of antidepressant medications to individual MDD patients using a readily-available inexpensive blood test. Additionally, results from the sub-study could validate the use of finger prick blood for the CRP test, providing an easier and faster alternative for busy clinical practice.

The second sub-study will investigate if pre- and post-treatment connectomic profiles obtained from resting electroencephalography (EEG) are able to predict differential antidepressant treatment response. EEG also offers clinical utility as a cost-effective and rapid means of assessing neurological activity. EEG biomarkers have demonstrated ability to predict response to different interventions in depression^{65, 66}. Further development of this capability has potential to rapidly advance personalized medicine.

To facilitate the understanding of the protocol, we define two commonly used terms in this protocol:

CRP-consistent antidepressant selection: participants with a baseline venous CRP level greater than or equal to 1 will be prescribed bupropion XL and participants with a baseline venous CRP level less than 1 will be prescribed escitalopram.

CRP-inconsistent antidepressant selection: participants with a baseline venous CRP level greater than or equal to 1 will be prescribed escitalopram and participants with a venous baseline CRP level less than 1 will be prescribed bupropion XL.

2.2. Study Aims

- *Primary Aim 1:* To compare the efficacy of CRP-consistent antidepressant selection versus CRP-inconsistent antidepressant selection on remission rates in patients with MDD.
- *Primary Aim 2:* To compare the efficacy of CRP-consistent antidepressant selection versus CRP-inconsistent antidepressant selection on improving social and occupational functioning.
- *Primary Aim 3:* To compare CRP-consistent antidepressant selection versus CRP-inconsistent antidepressant selection on adverse antidepressant treatment effects.

- *Sub-Study Aim 1:* To investigate if capillary blood provides a valid and reliable CRP measurement by comparing the levels of POC CRP obtained by capillary blood (finger prick) with those obtained by venous blood (blood draw).
- *Sub-Study Aim 2:* To evaluate the ability of various measures of functional network connectivity obtained from resting EEG to predict treatment response.

3. Study Design

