6.1. Outcome Measures

The primary study endpoint will be remission rates based on the 16-item Quick Inventory of Depressive Symptomatology, Self-Report (QIDS-SR), which will be extracted from the 30-item Inventory of Depressive Symptomatology (IDS-SR). QIDS-SR measures MDD severity; a score of 5 or less is considered remission. The secondary study endpoints will be: a) improvement in social and occupational function according to the 5-item self-administered Work and Social Adjustment Scale and b) side effect measures using the 3-item Frequency, Intensity, and Burden of Side Effects Rating (FIBSER) scale.

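### Does calling functioning and adverse effects Primary Aims 2 and 3 in Section 2.2 upset the single primary endpoint set in Section 6.1?

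*Protocol*

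**What the plan says.** Section 2.2 (Study Aims) lists three aims under the label primary, then two sub-study aims, and no secondary aims.

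- The first of the three concerns remission on the depression scale.
- The second, numbered as Primary Aim 2, takes up functioning and is worded "To compare the efficacy of CRP-consistent antidepressant selection versus CRP-inconsistent antidepressant selection on improving social and occupational functioning".
- The third, which carries the same primary label, turns to tolerability and is worded "To compare CRP-consistent antidepressant selection versus CRP-inconsistent antidepressant selection on adverse antidepressant treatment effects".

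Section 6.1 (Outcome Measures) ranks the endpoints. It opens with "The primary study endpoint will be remission rates", measured on the QIDS-SR with a score of 5 or less counting as remission. Functioning comes next, one tier down: "The secondary study endpoints will be: a) improvement in social and occupational function according to the 5-item self-administered Work and Social Adjustment Scale". Listed as item b in that same lower tier is the tolerability outcome, described as "side effect measures using the 3-item Frequency, Intensity, and Burden of Side Effects Rating (FIBSER) scale".

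Section 2.1 (Study Overview) states one main objective for the trial and then adds: "Additionally, two optional sub-studies will be available for participants to enroll in". Its short list of definitions, introduced by "we define two commonly used terms in this protocol", covers only CRP-consistent and CRP-inconsistent selection. It does not define a primary aim.

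**The concern.** The same two outcomes are primary under one heading and secondary under another. The three aims match the three endpoints of Section 6.1 one to one and in the same order, so it is not enough to say that aims and endpoints are different things.

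What would be at stake is the hierarchy of claims. The trial is open label with 70 participants, and its endpoints are self-reported. If remission showed no difference, a favourable WSAS or FIBSER result could be presented as meeting a primary aim by pointing to Section 2.2. If all three outcomes really were primary and each was tested at the full level, the chance of a false positive claim would exceed the nominal level. An SAP author working from this protocol would also have to decide which section to follow.

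**Working it through.** The protocol gives no alpha, power or effect size for these outcomes, so there is no stated figure to reproduce. The check is mainly a comparison of text.

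**1. What each section decides.**

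| Outcome | Section 2.2 | Section 6.1 |
|---|---|---|
| Remission | Primary Aim 1 | Primary endpoint (QIDS-SR) |
| Functioning | Primary Aim 2 | Secondary endpoint a (WSAS) |
| Adverse effects | Primary Aim 3 | Secondary endpoint b (FIBSER) |

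Section 2.2 names no instrument, threshold or test. Section 6.1 names the instruments, and it is the only text that orders the endpoints. It speaks of the primary endpoint in the singular and of the secondary endpoints in the plural.

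**2. What primary means at the level of aims.** Three places bear on this.

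- Section 2.2 sets primary aims against sub-study aims and has no third tier.
- Section 2.1 makes the same division: one main objective, then two optional sub-studies.
- Section 11 (Potential Benefits) refers to the finger-stick comparison, which is a sub-study, as the secondary analysis.

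All three fit a usage in which primary, when applied to an aim, means belonging to the main study. On that usage a primary aim can be served by a secondary endpoint, and Sections 2.2 and 6.1 do not conflict.

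**3. Whether other text points to three primary endpoints.** None does. The directional expectation in Section 3.1 is stated for remission only, and no section calls WSAS or FIBSER a primary endpoint.

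**4. Size under the adverse reading.** Assume three separate primary tests, each at an unadjusted two-sided 5%, independent, with no true effect and any one sufficing for success:

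- Familywise error = 1 − (1 − 0.05)³ = 1 − 0.857375 = 0.1426, about 14%.
- Upper bound without independence = 3 × 0.05 = 0.15.
- With remission as the only primary endpoint, as Section 6.1 has it, the error is 0.05 and the excess is zero.

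The alpha, the independence, the three-way test and the any-one-suffices rule are all assumptions. Independence is doubtful, since remission, functional impairment and side-effect burden are measured in the same patients. The figure describes a design that the protocol does not set out.

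**The case for a change.** The strongest argument for acting is that the repair is almost free. Relabelling two aims, or adding one sentence, would remove any room for argument before results are known, and would do so on either reading. It can also be said that the vocabulary is unsettled: secondary means a sub-study in Section 11 but WSAS and FIBSER in Section 6.1, neither sense is defined, and the reader has to infer the hierarchy. Nor is this something left for an SAP to supply, because both statements stand in the protocol itself.

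Most of this is accurate. The labels do differ, no sentence reconciles them, and a tidier text would use one vocabulary.

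What does not stand is the step from untidy labels to a risk for the analysis. The reader does not have to infer the endpoint hierarchy, because Section 6.1 states it; only the meaning of the aim label is left to inference. A claim that WSAS or FIBSER met a primary endpoint would be contradicted by Section 6.1 as it is now written. A low cost of editing is also not a gain: after the edit, the primary endpoint, the secondary endpoints, the sample size and the data collected would all be the same as before.

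**Conclusion.** The inconsistency is one of labelling, and it calls for no change to the plan. Section 6.1 fixes remission as the single primary endpoint, with functioning and side effects secondary. Sections 2.1, 2.2 and 11 support reading a primary aim as a main-study aim. An analyst following the protocol would arrive at the same hierarchy with or without a clarification, so no analysis, result or sound conclusion depends on it.

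The excess type I error is zero when Section 6.1 governs, and nothing in the protocol suggests that it does not. The 14% figure holds only under the assumptions listed with the calculation and should not be cited as a property of this trial.

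The conclusion rests on Section 6.1 being the operative statement of endpoints. It would need another look only if the SAP, which is not at hand, treated functioning or side effects as further primary endpoints. Should the protocol be amended for other reasons, the wording of Section 2.2 could be tidied then as a courtesy to readers.

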3.1. Overview

The current study is single site, randomized, open label 8-week clinical trial comparing the efficacy of CRP-consistent antidepressant selection vs CRP-inconsistent antidepressant selection. Venous levels of CRP will be measured by an FDA cleared Point of Care Smart analyzer (Diazyme Laboratories) and/or Quest Diagnostics, which provides the CRP concentration within few minutes. The study will use a stratified randomization (i.e. separate randomization schemes for patients with POC CRP ≥ 1 and POC CRP < 1). This will assure that the four study groups have similar sample sizes: 1) escitalopram with CRP < 1 , 2) bupropion-XL with CRP < 1 , 3) escitalopram with CRP ≥ 1 , 4) bupropion-XL with CRP ≥ 1 . We anticipate that participants with higher inflammation (CRP ≥ 1) will have higher remission rates with bupropion-XL than escitalopram, while individuals with low levels of systemic inflammation (CRP < 1) will remit more frequently with escitalopram when compared to those treated with bupropion XL. A sub-study will compare POC CRP levels based on the blood source: venous blood obtained by venipuncture vs capillary blood obtained via fingerstick.

3.2. Methods

70 eligible subjects will be assigned to one of two groups based on their baseline venous CRP level: CRP < 1 or CRP ≥ 1 . Participants in both groups will then be randomly assigned in a 1:1 fashion to one of two treatment arms: a) CRP consistent antidepressant selection or b) CRP inconsistent antidepressant selection. All subjects will be followed for 56 (+/- 3) days (8 weeks) to examine the efficacy of the study treatments. The treatment phase is followed by a remote follow-up call and electronic self-report questionnaires at 12 weeks.

3.3. Study Population

Number of Subjects

70 subjects will enter the open-label treatment phase of this single site study at the Center for Depression Research and Clinical Care. This trial will be conducted according to the U.S. FDA guidelines and the Declaration of Helsinki. IRB-approved written informed consent will be obtained from all patients before any protocol-specified procedures are carried out. The subjects will be drawn from an outpatient sample of patients with MDD, diagnosed with the use of the Mini International Neuropsychiatric Interview (MINI).

3.4. Subject Eligibility

Inclusion Criteria

A subject will be eligible for inclusion only if all of the following criteria are met:

- Women and men ages 18-65
- Diagnosis of Major Depressive Disorder according to Diagnostic and Statistical Manual of Mental Disorders, Fifth Edition (DSM-5) criteria confirmed by the Mini International Neuropsychiatric Interview (MINI).
- Have a score of 14 or higher on the Hamilton Scale for Depressive Symptomatology as assessed by trained clinicians.

Exclusion Criteria

A potential participant will NOT be eligible for participation in this study if any of the following criteria are met:

- Any antidepressant use within the last 8 weeks
- Active infection or uncontrolled autoimmune disease
- Currently on oral corticosteroids or active immune suppressive therapy (methotrexate, cyclosporine, anti-cytokines medications, etc. Note that nonsteroidal anti-inflammatory drugs - NSAIDs - will be allowed).
- Current diagnosis of uncontrolled HIV, hepatitis C or significant immunodeficiency
- Subject has a history of moderate or severe substance or alcohol use disorder according to DSM-5 criteria, except nicotine or caffeine, within 3 months before signing informed consent form.
- Positive urine drug test for illicit substances or substances used out of the context of prescription
- Cognitively unable to give informed consent
- Pregnant or breastfeeding women, women of childbearing potential who are not using an accepted means of birth control, or women with a positive urine pregnancy test
- History of seizure disorder
- Previous significant adverse reaction to escitalopram or bupropion
- History of non-response to adequate doses of escitalopram or bupropion XL
- Current use of concomitant psychotropic agents (anticonvulsants, benzodiazepines, hypnotics, opiates, triiodothyronine (T3), modafinil, psychostimulants, buspirone, melatonin, folate, L-methylfolate, s-adenosyl methionine, lithium) not on the same dose for at least four weeks prior to study entry or who do not agree to continue at the same dose during the acute phase of the study.
- Lifetime history of bipolar disorder, schizophrenia, schizoaffective disorder or other psychotic disorder except for Major Depressive Disorder with psychotic features in prior episode.
- Current anorexia nervosa or bulimia nervosa per Mini International Neuropsychiatric Interview (MINI).
- Suicidal ideation of the degree that, in the opinion of the evaluating clinician, participation in the study would place them at significantly increased risk of suicide
- Unstable medical issues of such degree that, in the opinion of the evaluating clinician, participation in the study would place them at significant risk of a serious adverse event

Rationale for the Inclusion/Exclusion Criteria

Eligibility criteria for this study have been carefully considered to ensure the safety of the study subjects and to ensure that the results of the study are meaningful in support of the research hypotheses. It is imperative that subjects fully meet all eligibility criteria.

4. Study procedures

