5.1. Overview

The current study will use two FDA-approved medication for MDD: escitalopram and bupropion-XL. Systematic reviews and meta-analyses have failed to find significant differences in treatment outcomes in head-to-head comparisons of SSRIs and bupropion. In this context, the treatment provided in this clinical trial is expected to have similar risks to standard clinical care.

Escitalopram is a widely-used SSRI, which is FDA-approved for MDD in people aged 12 or older.⁴⁰ The efficacy is similar to other SSRIs but escitalopram is known for fewer side-effects and fewer pharmacological interactions making it well-tolerated and commonly used in clinical practice.⁴¹ The medication is commercially available in the generic form or under the brand name Lexapro. The generic medication will be provided in this study. The compound will be obtained from a commercial pharmacy. Since this is study is open-label, the medication will be dispensed to the participants in its usual commercial form. We will provide escitalopram in tablets of 5 mg, 10 mg, 15 mg and 20 mg.

Bupropion is a commonly used norepinephrine-dopamine reuptake inhibitor that is FDA-approved for MDD.⁴¹ Its antidepressant effects are comparable to SSRIs and other antidepressants.⁴²⁻⁴⁴ Bupropion has good overall tolerability.⁴⁵ Bupropion is commercially available in the generic form as well as under the brand names Wellbutrin, Zyban and Aplenzin. The medication comes in three formulations: regular bupropion, bupropion sustained-release (SR) and bupropion extended-release (XL). Bupropion-XL will be provided in this study (tablets of 150 mg and 300 mg). This formulation has the advantage of being used just once a day, while the other formulations need to be taken twice or three times a day. In addition to a better dosing schedule, bupropion-XL has theoretically fewer side-effects.⁴⁴

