6.3. Clinical, General Health, and Medical History Surveys

Self-Administered Comorbidity Questionnaire (SCQ): The SCQ assesses the presence of medical problems, whether treatment is received for the condition, and whether or not the condition limits functioning. Each question is answered on a yes/no basis. Each affirmative response to the three items per medical condition is coded as a 1, with the total score being the sum of all positive responses. The medical conditions specified on the SCQ include: heart disease, high blood pressure, lung disease, diabetes, ulcer or stomach disease, kidney disease, liver disease, anemia or other blood disease, cancer, depression, arthritis, thyroid disease and back pain.

Prior and Concomitant Medications: The Prior and Concomitant Medications form assesses prescribed and certain over-the-counter medications taken by the participant. The Prior and Concomitant Medications form will be administered at the baseline visit and at each visit thereafter, if the participant endorses a change in medication status.

Antidepressant Treatment Response Questionnaire (ATRQ): clinician-rated scale used to determine treatment resistance in MDD. The MGH ATRQ defines 6 weeks on an adequate dose of antidepressant medication as an adequate duration of treatment. It also provides specific operational criteria for adequate dosage for each of the most commonly used antidepressants.⁵²

Fagerstrom Test of Nicotine Dependence: The Fagerstrom Test of Nicotine Dependence consists of six items that test for dependence to nicotine. Sample items include "How soon after you awake do you smoke your first cigarette?" with answers including "within 5 minutes", "6-30 minutes", "31-60 minutes" and "after 60 minutes". A scoring algorithm has been created for all items in order to denote ranges of severity of dependence, including "very low dependence," "low", "moderate", "high", and "very high" levels.⁵³

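### The non-response exclusion names bupropion XL only, so on a literal reading it admits patients whom another bupropion formulation has already failed; the effect on the primary contrast is small

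*Protocol*

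**What the plan says.** Two neighbouring exclusion criteria in Protocol section 3.4 deal with past experience of the study drugs. The first excludes "Previous significant adverse reaction to escitalopram or bupropion" and names no formulation. The second excludes "History of non-response to adequate doses of escitalopram or bupropion XL" and names one.

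Section 5.1 describes bupropion as a single drug: "The medication comes in three formulations: regular bupropion, bupropion sustained-release (SR) and bupropion extended-release (XL"). The trial supplies the XL form. The differences given for XL are once-daily use and tolerability: "In addition to a better dosing schedule, bupropion-XL has theoretically fewer side-effects". No difference in efficacy between formulations is stated.

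The only other exclusion based on antidepressant history is "Any antidepressant use within the last 8 weeks", which does not reach further back. The Antidepressant Treatment Response Questionnaire (ATRQ), described in section 6.3 as a "clinician-rated scale used to determine treatment resistance in MDD", is scheduled at screening in Table 1, but no eligibility criterion refers to its result. The rationale after the criteria requires that they be met in full.

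**The concern.** If XL is only a formulation, failure on SR or regular bupropion is failure on the same drug. Applied as written, the criterion lets such a patient in and, under 1:1 allocation within the CRP stratum, gives an even chance of treatment with bupropion again. A patient with adequate-dose non-response to escitalopram never reaches randomisation. Known non-responders to the two study drugs are therefore screened unequally.

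Two things are at stake. First, section 3.1 states expectations within each stratum: bupropion XL better at CRP ≥ 1, escitalopram better at CRP < 1. Known bupropion non-responders lower bupropion remission in both strata. That works against the stated expectation in the high stratum and in its favour in the low stratum. Second, some patients would be re-exposed to a drug that has already failed them, in an open-label trial with a self-reported primary endpoint.

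Such patients are plausible. Section 7.2 recruits from psychiatric practices, from a cohort with lifetime or current mood disorder and from former research participants, and section 3.4 sets no limit on the number of earlier failed treatments.

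**Working it through.** **Reading the text**

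1. Adverse-reaction criterion: bupropion, no formulation. Non-response criterion: bupropion XL.
2. Section 5.1: regular, SR and XL are forms of one medication, separated by dosing convenience and tolerability. Nothing there suggests that failure on SR says little about XL. One of the two trials that section 5.3 cites for its medication schedule is, by its title in the reference list, a pilot of escitalopram with bupropion-SR, so the protocol itself carries SR experience over to XL.
3. No other criterion fills the gap: the recent-use exclusion stops at 8 weeks, and the ATRQ is collected without a rule attached.

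On the literal text, then, an earlier adequate-dose failure of SR or regular bupropion does not exclude.

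**Size**

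The protocol states no figure on this point, so there is none to reproduce. Inputs from the document: 70 patients (section 3.3) and 1:1 allocation within each CRP stratum (section 3.2). About 70/2 = 35 therefore receive bupropion XL, or 70/4 = 17.5 per stratum-by-drug cell if the strata are equal.

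Assumed inputs, none of them given in the protocol:
- f, the share of enrolled patients with an earlier SR or regular bupropion failure: 3% to 10%, the same in both strata.
- d, the amount by which their remission on bupropion is lower: 20 to 30 points, with no corresponding drop on escitalopram.
- w, the share of patients with CRP ≥ 1: 0.3 to 0.7.

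Expected number of such patients on bupropion XL: 35 × 0.03 = 1.05 to 35 × 0.10 = 3.5.

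Shift in bupropion remission, and so in bupropion minus escitalopram, within a stratum: −f × d.
- Low end: 0.03 × 20 = 0.6 points.
- High end: 0.10 × 30 = 3.0 points.

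Shift in the pooled contrast, CRP-consistent minus CRP-inconsistent. Bupropion is the consistent drug at CRP ≥ 1, so the contrast there falls by f × d. It is the inconsistent drug at CRP < 1, so the contrast there rises by f × d. Weighting by stratum size gives −w·f·d + (1 − w)·f·d = −f·d·(2w − 1).

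| w | f·d = 0.6 | f·d = 3.0 |
|---|---|---|
| 0.3 | +0.24 | +1.2 |
| 0.5 | 0 | 0 |
| 0.7 | −0.24 | −1.2 |

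For scale, take 35 per arm and an assumed remission rate p of 30% to 40%. The standard error of the difference is √(2p(1 − p)/35): √(2 × 0.30 × 0.70/35) = 11.0 points and √(2 × 0.40 × 0.60/35) = 11.7 points. The largest pooled shift, 1.2 points, is about a tenth of that.

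**The case against.** **The wording may be loose naming.** The protocol moves freely between the two names. Section 5.1 introduces bupropion as a norepinephrine-dopamine reuptake inhibitor, and section 5.2 says the same of bupropion XL before reverting to the shorter name. The text does not settle what was intended, and this stands. It does not remove the point: if every formulation was meant, the criterion is misworded and screeners may apply it differently; if XL only was meant, the contrast with the neighbouring criterion is unexplained.

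**The randomised comparison is not biased.** A reader might infer that the gap invalidates the comparison of arms. It does not. Eligibility is settled before randomisation, so earlier bupropion failures fall equally, in expectation, on both arms of a stratum. The population being compared changes; the validity of the comparison does not.

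**One patient could seem to matter a great deal.** In a cell of 17.5, one patient is worth 1/17.5 = 5.7 points. Using that as the effect assumes a certain remission turned into a certain non-remission. With a drop of 20 to 30 points, one such patient moves the cell by 20/17.5 = 1.1 to 30/17.5 = 1.7 points in expectation.

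**The asymmetry has limits.** The requirement of adequate doses applies to both drugs, so it would be wrong to infer that every past escitalopram failure is excluded. Nor does any criterion exclude failure on other SSRIs, although sections 1.3, 1.4 and 5.1 frame the question as SSRIs against bupropion. The net imbalance in treatment history between the two drugs therefore has no established direction.

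**Screening makes the history visible.** Psychiatric history, prior medication and the ATRQ are all taken before randomisation, so an investigator would often see an earlier bupropion failure. But visibility is not a rule, and the criteria are to be applied in full as written.

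**Conclusion.** The inconsistency is real on the text. Two adjacent criteria name the same drug differently, section 5.1 gives no reason for the difference, and nothing else in section 3.4 excludes an earlier adequate-dose failure of SR or regular bupropion. Whether the restriction was deliberate cannot be told from the document.

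The consequence is modest. On the assumed ranges, bupropion remission within a stratum falls by about 0.6 to 3 points. The pooled contrast of Primary Aim 1 shifts by about 0 with equal strata and by at most about 1.2 points in either direction with a 30:70 split. These figures rest on assumed rates of earlier failure and assumed loss of remission, and on both being equal across strata; unequal rates would make the cancellation less complete. The document does not support a claim that the primary result would be materially distorted. The gain from correcting the text lies in the within-stratum drug comparisons of section 3.1, in uniform screening, and in not re-exposing patients to a drug that has already failed them.

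**What to change.** Reconcile the two adjacent criteria in section 3.4 with section 5.1, so that the non-response criterion refers to bupropion in the same sense as the adverse-reaction criterion: any formulation, unless the sponsor gives a reason for XL only. State that prior non-response is determined from the ATRQ at screening, which by section 6.3 already carries operational definitions of adequate dose and duration.

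The cost is one phrase in an amendment and a few extra screen failures. No procedure is added. Eligibility has to be settled in the protocol, because an analysis plan cannot undo an enrolment. If patients have already entered under the present wording, the ATRQ data can show how many had an earlier bupropion failure, which would replace the assumed f with a count.
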